6.3. Prior to Discharge or Transfer to Another Hospital or Hospital Department

No study-related actions, unless driven by a sudden medical need, are required before a subject will be either discharged or transferred to another hospital department or hospital such as a rehabilitation clinic; however, discharge date needs to be captured in the eCRF.

6.4. Continued Treatment Visits

For all subjects randomized to VKA, all INR measurement shall be performed by local accredited/certified labs at a frequency determined by the subject's treating physician (monthly preferred). Trained and certified subjects may perform INR testing themselves using an approved point-of-care device but need to provide the results to the Investigator and the results need to be recorded in the eCRF.

- Dose adjustments in VKA will be made to achieve and maintain an INR of 2.0 to 3.0 (numbers inclusive) [Japan: 1.6 to 2.6 in subjects aged ≥ 70 (numbers inclusive)] throughout the study.

For all subjects, study visits (either as on-site or at the subject's current place of living, must be conducted by the Investigator or their appropriately trained designee) at 3 months (± 14 days), 6 months (± 14 days), and at 6 month intervals (± 14 days) thereafter through the end of the study which may be 36 months or longer (i.e., event driven study).

The following procedures will be performed during study visits:

- Check and record any changes in concomitant medication
- Assessment and recording of (S)AEs and suspected clinical events since last visit
- Assessment of any hospitalization for cardiovascular causes (such as shock, arrhythmia, cardiac rupture, stroke, aneurysms, stent occlusions, etc.) or bleeding
- Record vital signs (blood pressure and heart rate after the subject has been resting at least 5 minutes in a sitting position; body temperature and weight)
- Only if medically necessary, 12-lead ECG and recording of the results
- For childbearing potential female subjects, a urine pregnancy test (e.g., dipstick test) will be performed at 3 months, 12 months, 24 months, and End of Treatment

Visits. Furthermore, pregnancy tests will be carried out whenever there are clinical indications for the existence of a pregnancy.

- Blood draw for analysis by an accredited/certified local laboratory for all subjects (see Section 9.9) or if results are available from standard of care and are within 15 days prior to the visit these values may be used instead of requiring an additional blood draw.
 - *The liver function panel needs to be run at the 6 Month and 12 Month Visits and if clinically necessary at other times.*
 - In subjects randomized to VKA, obtain the subject's INR records from previous visit(s) through to the current visit and adjust dose as necessary to obtain/maintain an INR of 2.0 to 3.0 (numbers inclusive) [Japan: 1.6 to 2.6 in subjects age ≥ 70 (numbers inclusive)]. INR measure is only mandated if the previous measurement was performed more than 3 months prior to this visit or the target INR has been shown difficult to achieve.
- Record all INR results for subjects on VKA since subject's last visit in eCRF (if not recorded earlier in the eCRF).
- Review and record study regimen compliance and drug interruptions
 - Collect any unused study medication
- Dispense Edoxaban and inform subjects that VKA and OAP will be provided or prescribed from the study site or treating physician, as needed. If approved by the local regulatory authority, site should re-dispense the VKA Patient Prescription Aid at each study visit. Review dosing records for all subjects, and VKA and APT therapy regime and prescription information. All dosing information should be recorded in source on the applicable logs, in EDC, and for Edoxaban only, also in IXRS.
- If echocardiogram (TTE or TEE) has been done at any time as medically indicated or as per local standard of care in the individual centers, the results will be recorded as specified in the eCRF.

At Months 3 and either Month 12 or at EOT (whichever comes first):

- Have the subject complete the PACT-Q2 and EQ-5D-5L questionnaire which will be provided separately to the sites. This should be done before other procedures are conducted.

6.5. End of Treatment (EOT) Visit

As an event driven study, the subjects will continue on treatment until the study is stopped (the end of the study) due to 320 adjudicated events (from approximately 2500 subject years) will have been reached, or they permanently discontinue from the study (for any reason). Subjects enrolled late in the study may be terminated from the study after a minimum of 6 months on treatment. The end-of-treatment (EOT) visit is the subject's last treatment visit independent of whether this is the end of the study or occurs at time of their withdrawal or discontinuation for any reason. Subjects will also have a Post-treatment Follow-up Visit 30 days (± 7 days) after the EOT Visit.

The following procedures will be performed:

- *If EOT is prior to 12 months, have the subject complete the PACT-Q2 questionnaire and EQ-5D-5L questionnaire; if after 12 months on treatment, this is not done as it was captured at 12 months.*
- Check and record any changes in concomitant medication
- Review and record study regimen compliance and drug interruptions
- Assessment and recording of (S)AEs and suspected clinical events since last visit
- Assessment of any hospitalization for cardiovascular causes (such as shock, arrhythmia, cardiac rupture, stroke, aneurysms, stent occlusions, etc.) or bleeding
- Record date/time of final dose of study medication
- Collect all unused study drug(s)
- For childbearing potential female subjects, a urine pregnancy test (e.g., dipstick test) will be performed.
- Draw blood for analysis by an accredited/certified local laboratory for all subjects see Section 9.9 or if results are available from standard of care and are within 15 days prior to the visit these values may be used instead of requiring an additional blood draw;
 - In subjects randomized to VKA, obtain the subject's INR records from previous visit(s) through to the current visit (inclusive)
- Physical examination (details under Section 6.2)
- Record vital signs (blood pressure and heart rate after the subject has been resting at least 5 minutes in a sitting position; body temperature, and weight)
- If not part of standard of care, a 12-lead ECG will be performed. The results of any ECG will be recorded in the eCRF
- If echocardiography (TTE or TEE) has been performed at any time as medically indicated or as per local standard of care for TAVI, the results will be recorded as specified on eCRF.
- Confirm consent to participate in Post Discontinuation/Follow-up Contact;

Transition subject to appropriate medication (Section 5.2.1)**Note: In subjects with early permanent discontinuation of the assigned therapy every attempt made to have the Follow-up Visit performed.**

6.5.1. Transition from Study Medication to Standard of Care VKA

Before transitioning to open-label VKA, all non-transition kit study supplies must be retrieved from the subject to avoid drug administration errors. For information on transitioning of medication, see Section 5.2.1.

The subjects on Edoxaban will use the Sponsor provided transition kit to transition from Edoxaban to a VKA. The choice of VKA will be made by the Investigator in consultation with the subject's personal physician and per local guidelines. More information on this transition from Edoxaban to open-label VKA is available in

Section 5.2.1. Subjects on VKA may be transitioned to another locally approved VKA following local guidelines.

6.6. Post-treatment Follow-up Visit

The Follow-up Visit will be 30 days (\pm 7 days) after the last study treatment.

The Follow-up Visit activities are listed below:

- Perform physical examination;
- Record vital signs (blood pressure and heart rate after the subject has been resting at least 5 minutes in a sitting position; body temperature, and weight);
- Check INR and recommend any dose adjustments to subject's personal physician;
- Blood draw for analysis by an accredited/certified local laboratory, the clinical laboratory tests (see Section 9.9) or if results are available from standard of care and are within 15 days prior to the visit these values may be used instead of requiring an additional blood draw;
- Assessment and recording of (S)AEs and suspected clinical events since last visit; Assessment of any hospitalization for cardiovascular causes (such as shock, arrhythmia, cardiac rupture, stroke, aneurysms, stent occlusions, etc.) or bleeding;
- Record any changes in concomitant medications;
- Confirm consent to participate in Post Discontinuation/Follow-up Contact;
- For childbearing potential female subjects, a urine pregnancy test (e.g., dipstick test) will be performed.

6.7. Post Discontinuation/Follow-up Contact

- Subjects (unless they refuse to participate) will be called approximately every 6 months (\pm 1 month) until the Sponsor determines the end of the study to assess the subject's vital status, occurrence of potential endpoint events, or any SAEs. This information may be obtained from relatives, public records, or the treating physician. Should the subject choose to not receive phone calls, the site may attempt to retrieve this information from viewing the subject's medical records or public records.

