MI	Myocardial infarction
mITT	Modified intention to treat
MLBCs	Major late bleeding complications
NACE	Net adverse clinical events
NSAID	Nonsteroidal anti-inflammatory drug
OAC	Oral anticoagulant(s)
OAP	Oral antiplatelet
PACT-Q	Perception of Anticoagulant Treatment Questionnaire
PCI	Percutaneous coronary intervention
P-gp	P-glycoprotein
PP	Per protocol
PT	Preferred Term
SAE	Serious Adverse Event
SAF	Safety analysis set
SAP	Statistical Analysis Plan
SAPT	Single antiplatelet therapy
SEE	Systemic embolic event
SmPC	Summary of product characteristics
SOP	Standard operating procedures
STS	Society of Thoracic Surgeons
SUSAR	Suspected Unexpected Serious Adverse Reaction
TAVI	Transcatheter aortic valve implantation
TEAE	Treatment-emergent adverse event
TEE	Transesophageal echocardiography or transesophageal echocardiogram
TEG	Thromboelastography
TIMI	Thrombolysis in Myocardial Infarction
TTE	Transthoracic echocardiography or transthoracic echocardiogram
ULN	Upper limit of normal
VKA	Vitamin K antagonist
WBCT	Whole blood clotting time
WHO	World Health Organization

DEFINITIONS SPECIFIC TO THIS PROTOCOL

Term	Definition for this protocol
Discontinuation	Permanent stoppage of study medication. The subject will not be allowed to restart study medication and should follow the transition procedures outlined in Section 5.2.1.1.2 or Section 5.2.1.2.2.
Interruption	A temporary stoppage of study medication. The subject is allowed to restart the study medication at the discretion of the Investigator.
End of TAVI	The clock for randomization starts with the removal of the sheath with hemostasis
End of Study	As an event driven study, enrollment will be stopped no later than at the attainment of a total of 320 subjects experiencing an adjudicated NACE across the combined treatment arms, and , the study will continue until the last subjects enrolled will have accomplished the minimum treatment duration of at least 6 months plus their Post-treatment Follow-up Visit. This Visit by the last subject enrolled will be defined as the end of the study (or common study end date [CSED]).
Major bleeding	Major bleeding is considered to include life-threatening and fatal bleeding.
Study drugs	Any study medication or prescribed oral antiplatelet (OAP) co-administered medication is defined within this protocol as a study drug.

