5.8.2. Subjects with Study Drug Interruptions/Discontinuations

The Investigator should call the CRO medical monitor in case of any questions regarding how to handle a study medication interruption and/or discontinuation.

Suspension/Interruption: The date/time of the last dose, the reason for the interruption, and other required details will be recorded in the eCRF. Reasons for interruption include but are not limited to: development of clinical contraindications for any study drug (according to the label of the respective drug). During each interruption of anticoagulant or antiplatelet therapy, subjects are evaluated to determine whether the subject can safely resume the study drug.

Discontinuation: The date/time of the last dose, the reason for the discontinuation, and other required details will be recorded in the eCRF. For some potential reasons for discontinuation of study drug see Section 5.8.1 and locally approved drug label.

During a study drug interruption or after study drug discontinuation, a subject can be placed on another antithrombotic therapy per local guidelines and Investigator discretion. All randomized subjects, including those who discontinued study medication, will be followed through the overall end of the study for the primary and secondary efficacy and safety endpoints and SAEs. If the subject has an onsite visit, it is expected that vital signs will be obtained along with any laboratory assessments deemed appropriate by the Investigator.

If a subject who discontinues study drug also withdraws consent, in writing, for participation in the study, the protocol-specified consent withdrawal procedures (Section 5.8.3) must be completed.

If the subject interrupts (or discontinues) study drug due to an AE, the Investigator will follow the event until it has resolved or stabilized.

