9.1. Adverse Event Collection and Reporting

All clinical AEs (see Section 9.3.1 for definitions) occurring after the subject signs the Informed Consent Form and up to 30 days after the last dose of study medication (i.e., the follow-up period), whether observed by the Investigator or reported by the subject, will be recorded on the Adverse Event eCRF page.

Subjects who permanently discontinue study medication but continue in the study will be followed up every 6 months for collection of vital status (not vital signs) including collection of SAE and/or endpoint event reporting until the end of study (see Section 6.7).

Medical conditions (including laboratory values/vital signs that are out of range) that were diagnosed or known to exist prior to Informed Consent will be recorded as part of medical history.

All serious adverse events (SAEs), are to be reported according to the procedures in Section 9.6.

- All laboratory results, vital signs, ECG, and any other imaging results or findings should be appraised by the Investigator to determine their clinical significance. Isolated abnormal laboratory results, vital sign findings, or ECG findings (i.e., not part of a reported diagnosis) should be reported as AEs if they are symptomatic, lead to study drug discontinuation, dose reduction, require corrective treatment, or constitute an AE in the Investigator's clinical judgment.
- At each visit, the Investigator or qualified designee will determine whether any AEs have occurred by evaluating the subject. Adverse events may be directly observed, reported spontaneously by the subject, or by questioning the subject at each study visit. Subjects should be questioned in a general way, without asking about the occurrence of any specific symptoms. The Investigator must assess all AEs to determine seriousness, severity, and causality, in accordance with the definitions in Section 9.3. The Investigator's assessment must be clearly documented in the site's source documentation with the Investigator's signature.

Always report the diagnosis as the AE or SAE term. When a diagnosis is unavailable, report the primary sign or symptom as the AE or SAE term with additional details included in the narrative until the diagnosis becomes available. If the signs and symptoms are distinct and do not suggest a common diagnosis, report them as individual entries of AE or SAE.

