11.4. Statistical Analyses

For each of the primary and secondary efficacy and safety endpoints, appropriate summary statistics (e.g., event rate) including 95% confidence interval (CI) will be provided.

For each of the endpoints, the time from reference date to the first occurrence of an event (based on CEC adjudication), is analyzed using a Cox proportional hazard model with treatment regimen as a factor and all the stratification factors from the randomization (IXRS) as covariates, dose adjustment [yes, no], to provide point estimates and 95% CI for the hazard ratio (HR). Depending on the analysis period used in the statistical analysis, subjects without an occurrence of an event will be censored at the last date of the analysis period or at the last date of known outcomes status. The latter is determined on an individual basis for subjects with incomplete follow-up.

The parameter estimate β ($= \ln(\text{Hazard ratio})$), its standard error, p-value, and 95% confidence limits are calculated according to the maximum partial likelihood method, with Breslow's approximation for ties (SAS PHREG procedure).

For time to first event analyses, cumulative event rates over time are summarized using the Kaplan-Meier method as appropriate.

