- k Assessment and recording of (S)AEs and suspected clinical events from the signing of the informed consent, and should be reported as soon as site personnel learn of the event and be reported within 24h of the Investigator's/site's awareness. Endpoint event and AE reporting should occur throughout the study and not be restricted to specific visits. If AST or ALT $> 3 \times \text{ULN}$ with simultaneous total bilirubin levels $> 2 \times \text{ULN}$ is observed, then ALP should be determined. Hospitalization due to cardiovascular events needs to be assessed.
- l When subjects are being transitioned to non-study medications, record the date and time of last administration of study medication, and collect all unused study medication. Subjects are transitioned to an approved OAC of the Investigator's or treating physician's choice. The Investigator will follow the transition strategy in the approved product label. Subjects who prematurely discontinue study OAC are requested to also complete the Post-treatment Follow-up Visit according to this schedule (See Section 5.2.1.1.2 and Section 5.2.1.2.2).

m EOT may occur at any time (e.g., at subject withdrawal or discontinuation) and will trigger this subject's Post-treatment Follow-up Visit.

n Female subject who are of child bearing potential.

o Female subject who are of child bearing potential. Furthermore, pregnancy tests are carried out whenever there are clinical indications for the existence of a pregnancy.

p All subjects who have taken study medication should be requested to consent for routine follow-up contact at 6-month intervals following termination of study drug. This will normally be as a phone contact until the end of the study is determined by the Sponsor. Should the subject choose to not receive phone calls, the site may attempt to retrieve this information from viewing the subject's medical records or public records.

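### Contacts with subjects off study drug run every 6 (±1) months from each subject's own EOT, and none is timed to the common study end date, so late outcomes may go unascertained; the likely effect is small and the remedy cheap

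*Combined protocol and SAP*

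**What the plan says.** **Promise.** Section 5.8.2 states that all randomized subjects, including those off study medication, "will be followed through the overall end of the study for the primary and secondary efficacy and safety endpoints and SAEs". Section 5.8 says the same. The synopsis (Study Duration) offers telephone contact or record review after EOT up to the common study end date (CSED).

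**Schedule.** After the 30-day visit, Section 6.7 provides that subjects "will be called approximately every 6 months (\pm 1 month) until the Sponsor determines the end of the study". Section 9.1 has the same interval: "Subjects who permanently discontinue study medication but continue in the study will be followed up every 6 months for collection of vital status", together with SAEs and endpoint events. Table 17.1, footnote p, sets the anchor: "routine follow-up contact at 6-month intervals following termination of study drug". It adds: "This will normally be as a phone contact until the end of the study is determined by the Sponsor". Footnote m allows EOT to fall at any time.

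**Study end.** The protocol's definitions place the CSED at the last enrolled subject's Post-treatment Follow-up Visit. Subjects still on drug when the study stops have an EOT visit and a 30-day visit (Section 6.5).

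**Analysis.** Under Section 11.4, "subjects without an occurrence of an event will be censored at the last date of the analysis period or at the last date of known" outcome status. Section 11.2 rules out imputation and ends the Overall Study Period at an estimated Month 36 or EOT (Visit 8). Section 9.5.1 has SAEs reported to study end, and Table 17.1, footnote k, asks for endpoint reporting throughout the study, not only at visits.

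**The concern.** Two clocks run independently. The calls follow the subject's own EOT; the study ends on a calendar date that has nothing to do with it. Nothing brings them together, so outcome ascertainment at study end is scheduled for subjects still on drug and left to chance for those who have stopped.

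Two things follow. Events after the last call may never be learned of. And ascertainment can become one-sided: an event that reaches the site after the last call can count, while an event-free subject is censored at last known status and contributes no matching time. Subjects who stop drug are those in whom an ITT noninferiority analysis most needs complete outcomes, and major bleeding, a primary endpoint of its own, is less likely than death to appear in public records.

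**Working it through.** **1. The plan's exposure figure.** Assume follow-up uniform over 6 to 36 months (minimum and intended maximum treatment duration). The mean is (6 + 36)/2 = 21 months, and 1400 × 21/12 = 2450 subject-years, close to the roughly 2500 in Section 6.5. The follow-up model is therefore reasonable for what comes next.

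**2. Length of the gap.**
- Maximum: 6 months on the nominal schedule, and just under 7 if the ±1 month runs from the previous call. If each window is set from EOT, the corner case (calls at 5 and 13 months) is just under 8. Only 3 to 4% of simulated gaps exceed 6 months.
- Mean: in a plain 6-month cycle, 6/2 = 3.0 months. In the first cycle the 30-day visit splits the interval: (1 × 0.5 + 5 × 2.5)/6 = 2.2 months. The overall mean lies between these. Simulation gives about 2.7 months with uniform 6 to 36 month follow-up and exponential stopping, and about 2.9 months with study end uniform over 1 to 30 months after EOT and the ±1 month windows applied.
- If the cut is a study-level EOT about one month before the CSED, the mean falls to about 2 months.

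**3. First NACE in the gap.** Subject-years in the gap = 1400 × share off drug × mean gap/12. The share is assumed, because the documents give none. Only subjects still free of NACE can add a first event. At 14%/year about 77% of the gap time is event-free in the simulation.

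| Off drug (assumed) | Subject-years in gap | of which event-free | × 14%/year | % of 320 |
|---|---|---|---|---|
| 15% | 46 | 35 | 4.9 | 1.5 |
| 25% | 77 | 59 | 8.3 | 2.6 |
| 40% | 125 | 96 | 13.4 | 4.2 |

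**4. Effect on power.** At 320 events the Schoenfeld formula gives 91.6% power at a hazard ratio of 0.95 and 82.1% at 1.0. Losing 4 to 15 events without replacement (10 to 40% off drug, 3-month gap, 75% event-free) leaves 90 to 91% and 80 to 82%.

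**5. Effect on the hazard ratio.** Take 1250 subject-years per arm (2500/2), a rate of 320/2500 = 0.128 and a true hazard ratio of 1. Let 20% of edoxaban and 30% of VKA subjects be off drug (assumed). Event-free gap time per arm is 700 × share × 0.75 × 3/12, that is 26.25 and 39.375 subject-years. Let q be the fraction of gap events that the site hears of:

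observed rate = [160 − gap × 0.128 × (1 − q)] / [1250 − gap + gap × 0.128 × q × 0.125]

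- q = 0: the ratio is 1, so there is no bias, only lost events.
- q = 0.5: edoxaban 158.32/1223.96 = 0.12935; VKA 157.48/1210.94 = 0.13005; ratio 0.9946, log −0.005.
- q = 1: edoxaban 160/1224.17 = 0.13070; VKA 160/1211.26 = 0.13209; ratio 0.9895, log −0.011.

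Simulation of the same scenario gives shifts up to about 0.013. Against ln 1.38 = 0.322, a shift of 0.005 is 2% and 0.013 is 4%. The standard error at 320 events is about 2/√320 = 0.112. With equal shares off drug and equal hearing of events the bias is about zero. If more edoxaban subjects stop, the sign reverses.

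**The case against.** **The primary window may not reach these calls.** Section 6.5 and footnote m make EOT the subject's last treatment visit, whenever it occurs. If the Overall Study Period ends at that visit, every Section 6.7 call lies outside it and the primary NACE and bleeding analyses are untouched. This stands as a condition on the point. The study-level reading fits the rest of the text better: Sections 5.8 and 5.8.2 require follow-up to study end, Section 11.2 asks for follow-up regardless of discontinuation, and a separate period already covers time on treatment. Even then, a subject whose Month 36 is already covered by a later call has no gap if the cut is Month 36.

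**Status need not stop at the last call.** The synopsis allows record review up to the CSED. Section 6.7 allows relatives, public records or the treating physician, and Section 5.8.3 offers public databases. This also stands, but these routes are optional and undated, so they do not ensure status at study end.

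**A stronger reading.** A reader might infer that outcomes of off-drug subjects end 6 to 7 months before the primary analysis cut and that the comparison is thereby tilted towards edoxaban. The documents do not support this. They do not define the cut as the CSED, 6 to 7 months is the tail of the gap, and they give no discontinuation rate, let alone one that differs by arm. Applying 14%/year to all the gap time (6, 11 or 17 events) would also count subjects who already had a NACE. Full hearing of late events combined with no knowledge of event-free subjects is an extreme case, since the same records often show both.

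**Conclusion.** The plan promises follow-up of every randomized subject to the end of the study, but its schedule does not time any contact there for those off drug. On the study-level reading the shortfall averages about 2.7 to 2.9 months, somewhat less if the cut is a study-level EOT.

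The consequences are modest: about 5, 8 or 13 first NACE at 15%, 25% or 40% off drug, a power loss of about two points or less at the mean gap, and a hazard-ratio shift of 2 to 4% of ln 1.38 in a scenario with unequal stopping. The results rest on an assumed discontinuation share, constant hazards, and stopping independent of events. Section 5.1.1 links the end of treatment to reaching a primary endpoint, which would lower the count of first events further.

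This does not threaten the noninferiority conclusion. It is worth correcting because it is cheap now and cannot be fully repaired once sites have closed.

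**What to change.** - **Section 6.7, Table 17.1 (Visit 10) and footnote p:** for every randomized subject no longer attending visits, replace the last 6-monthly call with a closing contact for vital status and endpoint events, within ±14 days of the announced study end date. Telephone, relative, treating physician, medical record or public record may serve, within the subject's consent. The sponsor announces the target date in advance.
- **Section 11.2:** define one calendar cut-off for the ITT Overall Study Period. Count only events on or before it, and censor event-free subjects at the earlier of that date and the closing contact. This also settles what EOT (Visit 8) means in the definition.
- **Sensitivity analysis:** for subjects without a closing contact, ignore events dated after their last completed scheduled contact.

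The cost is a wording change and at most one re-timed call per off-drug subject: 1400 × 15% to 40% = 210 to 560 calls over about 200 sites, or roughly one to three per site. No new visits, procedures or staff are needed.
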